- ^a Patients will return to the clinic or will be contacted for a safety follow-up assessment 30 days \pm 3 days after the last dose of study drug was taken; or earlier if subsequent therapy for advanced malignancy is initiated prior to 30 days \pm 3 days.
- ^b Patients or their legally authorized representatives will be contacted every three months (\pm 7 days) until death, end of the study, or patient withdrawal of consent, whichever comes first. Survival and subsequent treatment status may be collected by public records, medical records, or by contacting the patient or their legally authorized representative by phone.
- ^c Full medical history at screening, only review/update of history at subsequent visits.
- ^d Oncologic history of the malignancy under study including prior regimens (duration of therapy, best response on therapy, date of discontinuation, and reason for discontinuation), surgery, and radiation therapy.
- ^e Physical examinations should be symptom driven after the Screening Visit.
- ^f Ophthalmological examinations will be performed by an ophthalmologist at screening, and whenever clinically indicated. In Part B, only patients in the ulixertinib arm need an ophthalmological exam. See section 10.1.5 for a full description of tests.
- ^g ONLY if the screening serum pregnancy test was performed more than 1 day previously.

- h After screening and baseline, if urine pregnancy test is positive, confirm with serum test.
- i Visit 2 clinical lab samples should be collected pre-dose if not done during Screening Visit within 72 hours of start of treatment.
- j Chemistry, hematology, and urinalysis. After Cycle 2, clinical labs to be performed prior to starting each new cycle or more frequently when clinically indicated at the investigator's discretion. See section 10.1.6 for a full description of test.
- k Patients with a normal ECG in Cycle 1 do not need to have repeat ECGs in subsequent cycles. Patients should be supine for 5 minutes prior to the ECG.
- l Tumor assessments will be made prior to dose initiation, at Visit 5, and then every 2 cycles. Patients who discontinue treatment for reasons other than progression will have assessments at the EOT visit (unless their previous assessment was performed within 28 days). The same imaging modality used for an individual patient (i.e. CT or MRI) at Screening should be maintained throughout the study.

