7.2 EXCLUSION CRITERIA

Patients who fulfill one or more of the following criteria will not be eligible for inclusion in this trial:

1. Gastrointestinal (GI) condition that could impair absorption of study medication (specific cases e.g., remote history of GI surgery, may be enrolled after discussion with the medical monitor) or inability to ingest study medication.
2. Uncontrolled or severe intercurrent medical condition.
3. Known uncontrolled brain metastases. Stable brain metastases either treated or being treated with a stable dose of steroids/anticonvulsants, with no dose change in the previous 4 weeks, can be allowed.
4. Having received any cancer-directed therapy (chemotherapy, hormonal therapy, biologic or immunotherapy, etc.) within 28 days or 5 half-lives (whichever is shorter) prior to the first dose of study drug. Patients previously treated with radiotherapy must have recovered from the acute toxicities associated with such treatment.
5. Major surgery within 4 weeks prior to first dose.
6. Any use of an investigational drug within 28 days or 5 half-lives (whichever is shorter) prior to the first dose of study drug. A minimum of 10 days between termination of the investigational drug and administration of study drug is required. In addition, any drug-related toxicity except alopecia should have recovered to Grade 1 or less.
7. Prior therapy with any ERK inhibitor (e.g. LY3214996, LTT462).
8. Groups 1-4: Prior therapy with any BRAF and/or MEK inhibitor (e.g. encorafenib, dabrafenib, vemurafenib, binimatinib, trametinib, cobimetinib) is excluded. Prior BRAF and/or MEK inhibitor therapy is permitted for Groups 5 and 6.
9. For Part B, agents targeting BRAF or MEK kinases and experimental agents are not permitted as physician choice.
10. Pregnant or breast-feeding women.

11. Any evidence of serious active infections. Patients are allowed to enroll if they have been fever-free for at least 48 hours and are on an active treatment that is not prohibited in Appendix 1.
12. Any important medical illness or abnormal laboratory finding that would increase the risk of participating in this study (based on the investigator's judgment).
13. A history or current evidence/risk of retinal vein occlusion (RVO) or central serous retinopathy (CSR).
14. Concurrent therapy with any other investigational agent.
15. Concurrent therapy with drugs known to be strong inhibitors or inducers of CYP1A2, CYP2D6, and CYP3A4.

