8.3 RANDOMIZATION

Part A is designed as an open-label study. All patients in Part A will receive treatment with orally administered ulixertinib. Patients in Part B will receive either treatment with orally administered ulixertinib or the physician's choice of treatment in a 2:1 ratio. In Part B, if a patient progresses on the physician's choice of treatment then they may crossover to the ulixertinib arm.

Part B randomization will be performed as total enrollment rather than on a site basis. Randomization/enrollment in both parts will be performed by using Interactive Voice/Web Response System (IxRS). Once written consent has been given by the patient, all inclusion/exclusion criteria must be checked by the investigator in order to confirm eligibility prior to IxRS randomization/enrollment procedures. In Part B, the IxRS will randomly assign the patient to one of the two treatment arms (ulixertinib or

the physician's choice of treatment). In both parts, the IxRS will assign the patient a unique patient identification number. This patient identification number will then be reported on all eCRF pages and in any study documents.

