10.1.5 Ophthalmology Examination

A full ophthalmic examination will be performed at the time points described in the SoA or when clinically indicated. They will include best-corrected visual acuity (BCVA), visual field examination (VF), intraocular pressure, external eye examination, and dilated fundoscopy. For additional details refer to study manual.

Any patient experiencing vision changes must stop taking ulixertinib and have an ophthalmic evaluation. Ulixertinib may be re-started when symptoms resolve.

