10.3.1.1 Visit 1 (Day -28 to -1); Screening

The following procedures will be performed at Visit 1 (Screening):

- Obtain written informed consent (before start of any study-related procedures that are not considered Standard of Care) including optional consents (Note: informed consent may be obtained up to -28 days to allow flexibility in scheduling of the screening procedures).

- Evaluate all inclusion and exclusion criteria to ensure that patients meet all inclusion criteria and none of the exclusion criteria.
- Record demographic data including date of birth (DOB), age, gender, race, and ethnicity. Where full DOB is collected, initials will not be used.
- Review medical history including all previous cancer treatments, best response to those cancer treatments, and reason for stopping them.
- Record prior and concomitant medications including start/stop dates, indication, dose, toxicities, and frequency taken within 30 days of Cycle 1, Day 1.
- Measure and record height and weight.
- Record vital signs. Measure body temperature, systolic / diastolic BP, and pulse rate.
- Perform and record physical examination.
- Assess and record performance status (ECOG) within 72 hours before start of treatment.
- Perform and record ophthalmology examination (ulixertinib patients only).
- Collect blood for a serum pregnancy test for female patients who are not postmenopausal or surgically sterile. If positive, repeat and confirm results prior to Visit 2. A second positive test will result in exclusion of the patient from the study.
- Collect blood samples for blood chemistries, hematology, and calculated creatinine clearance (using Cockcroft-Gault) within 72 hours before start of treatment. Analyze, review, and report any clinically significant abnormalities to the medical monitor before dosing.
- Collect urine samples for urinalysis within 72 hours before start of treatment.
- Obtain a 12-lead electrocardiogram (ECG), and echocardiogram (ECHO) or multi-gated acquisition (MUGA) for left ventricular ejection fraction (LVEF).
- Assess and record current disease status within 28 days. Tumor assessments will be made by CT/MRI/Physical Exam.

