- PART A only: Tissue biopsy within -28 days of Visit 1 (required unless investigator and medical monitor deems collection inadvisable). If a patient has undergone a biopsy within \leq 6 months and has not received any anticancer treatment since undergoing the biopsy, archival tissue from this biopsy may be used to fulfill screening tissue requirements.
- Complete Screening/Enrollment Form and submit to medical monitor for review prior to treatment of patient.
- For Part B only, prior to Visit 2, obtain a randomization code as outlined in Section 8.3.

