10.3.1.2 Visit 2 (Day 1 ± 0); Baseline/Drug Dispensing/Initiation of Treatment

The following procedures will be performed at Visit 2 (Baseline):

- Review Screening/Enrollment Form to confirm consent to enroll was obtained from medical monitor or sponsor.
- Review all inclusion and exclusion criteria to ensure that patients meet all inclusion criteria and none of the exclusion criteria.
- Review medical history for any changes since Screening Visit.
- Record medications including start/stop dates, indication, dose, toxicities, and frequency for any changes since Screening Visit.
- Measure and record weight.
- Record vital signs. Measure body temperature, systolic / diastolic BP, and pulse rate.
- Assess and record performance status (ECOG), if not done during Screening Visit, within 72 hours of start of treatment.
- ONLY if the screening pregnancy test was performed more than 1 day previously, collect blood for a repeat serum pregnancy test for female patients who are not postmenopausal or surgically sterile.
- Collect pre-dose blood samples for blood chemistries, hematology and creatinine clearance if not done during Screening Visit within 72 hours of start of treatment.
- Collect pre-dose urine samples for urinalysis.
- PART A only: Collect pre-dose blood samples for pharmacodynamic (PD) and ctDNA analyses.
- Administer first dose of ulixertinib.
- PART A only: Collect 4-hour (\pm 10 minutes) post-dose blood samples for pharmacodynamic analyses.
- Assess and record AEs.
- Dispense study drug and instruct patients how to take study drug, daily every 12 hours \pm 2 hours with at least 8 ounces of water and food.
- Inform patients of the potential photosensitizing effects of ulixertinib and instruct them to avoid sunlight and wear protective clothes, sunglasses, and apply sunblock when outside, including when driving a car.

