- Perform urine pregnancy test for female patients who are not postmenopausal or surgically sterile. If urine test positive, test, collect blood for a serum pregnancy test.
- Assess and record disease status (every 2 cycles).
- Assess and record AEs.
- Obtain all unused study drug from patient.
- Assess study drug compliance by reviewing pill count.
- Dispense study drug supply for self-dosing. Extra doses may be dispensed at the investigator's discretion to ensure continuous dosing.

10.3.4 Description of Study Visits for Patients Enrolled in Part B and Receiving Physician's Choice of Treatment

Study procedures for patients enrolled in Part B and randomized to physician's choice of treatment will be the similar to those for patients receiving ulixertinib; however, no pharmacokinetic or pharmacodynamic samples will be collected in Part B, and an ophthalmology examination will be performed only for patients receiving ulixertinib. Appropriate SoC monitoring can be completed at the discretion of the investigator. If clinical experience gained in Part A requires significant deviations in Part B from the procedures in Part A, these changes will be addressed in a protocol amendment.

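### Part B limits the screening eye examination to the ulixertinib arm, so one exclusion criterion cannot be settled before randomization as Section 8.3 requires, and an exclusion found only by that examination can fall in one arm alone

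*Protocol*

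**What the plan says.** **Eligibility before allocation.** Protocol Section 8.3 states that "all inclusion/exclusion criteria must be checked by the investigator in order to confirm eligibility prior to IxRS randomization/enrollment procedures".

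**The criterion.** Exclusion 13 (Section 7.2) covers a history, current evidence or risk of retinal vein occlusion (RVO) or central serous retinopathy (CSR). It has no limit by arm.

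**The examination.** The full ophthalmic examination in Section 10.1.5 includes dilated fundoscopy and is scheduled at screening. Three places restrict it in Part B:
- Schedule of Activities, footnote f: "In Part B, only patients in the ulixertinib arm need an ophthalmological exam".
- Section 10.3.1.1 lists it at Visit 1 for ulixertinib patients only.
- Section 10.3.4: "an ophthalmology examination will be performed only for patients receiving ulixertinib".

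**Timing.** Part B is open-label (Section 11.3). The Schedule of Activities marks randomization in the screening column, Day -28 to -1. Section 10.3.1.1 says: "For Part B only, prior to Visit 2, obtain a randomization code as outlined in Section 8.3". At Visit 2, Section 10.3.1.2 asks sites to "Review all inclusion and exclusion criteria to ensure that patients meet all inclusion criteria and none of the exclusion criteria".

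**Analysis.** The full analysis set (FAS), used for all efficacy analyses, requires at least one dose (Protocol 11.4.1; SAP Section 8). Section 9.3 treats discovery of ineligibility as withdrawal.

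**The concern.** An examination restricted to one arm of a randomized comparison cannot be arranged until the arm is known. If its result can exclude a patient, the exclusion comes after allocation and can happen in only one arm. A patient with silent retinal disease would be removed if allocated to ulixertinib and retained if allocated to physician's choice, where nobody looks.

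The wider timing raises a second, weaker issue. Eligibility decisions in either arm may be taken by staff who already know the allocation.

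At stake is the comparability of the randomized groups for the Part B primary endpoint, PFS. There is also a practical problem: each site would have to decide for itself which instruction to break.

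**Working it through.** **1. Can the instructions all be followed?** Section 8.3 puts every criterion before IxRS. Exclusion 13 includes current evidence of RVO or CSR, which fundoscopy can reveal. Footnote f, 10.3.1.1 and 10.3.4 give that examination only to ulixertinib patients, whom IxRS itself creates. Before randomization a site can therefore judge exclusion 13 only on history or existing findings. If the examination bears on the criterion, the passages conflict.

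**2. Does it reach the primary analysis?** The sequence is allocation, one-arm examination, Visit 2 review, first dose, FAS. A patient ruled out before dosing never enters the FAS. (I read study medication as covering the assigned comparator, so that a treated control stays in.) Section 9.3 also says that early withdrawals will be evaluated for efficacy, which does not fit a dosed-only FAS for someone never dosed.

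**3. What else can follow allocation?** Randomization may occur on any day from -28 to -1. Labs and ECOG are due within 72 hours of treatment and may be done at Visit 2 if not done at screening. The serum pregnancy test is repeated at Visit 2 if the screening test is more than a day old. All of these can come after allocation, in either arm.

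**4. The plan's own sample size, for scale.** Inputs from Section 11.2.2: two-sided 5%, 80% power, 2:1, control median 1.7 to 8.5 months doubled on ulixertinib (HR 0.5 if exponential), 24 months' accrual, 18 months' further follow-up, 10% loss.
- Events (Schoenfeld) = (1.960 + 0.842)² / [(2/3)(1/3)(ln 0.5)²] = 7.85 / 0.1068, or 74.
- Event probability with uniform accrual: 0.997 at 1.7 months and 0.762 at 8.5 months.
- N = 75 to 98 without loss, 84 to 109 dividing by 0.9, and 76 to 100 with loss as a hazard reaching 10% by month 42.

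The stated 80 to 100 is broadly reproduced. The documents do not say how loss was handled.

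**5. Size of a one-arm exclusion.** The documents give no rate of examination-detected RVO or CSR at screening. The figure of under 1% of 115 patients for RVO in Section 4.2.1 is an on-treatment rate. I assume 1% to 10% of the ulixertinib arm. At 2:1, N = 80 gives about 53 on ulixertinib and 27 controls; N = 100 gives 67 and 33.

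| N, control median | Removed at 1% to 10% | Power with none, 5%, 10% removed |
|---|---|---|
| 80, 1.7 months | 0.5 to 5.3 | 79.0%, 78.3%, 77.6% |
| 100, 8.5 months | 0.7 to 6.7 | 77.2%, 76.6%, 76.0% |

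Power here counts events as 0.9 × N × event probability. The largest loss is 79.0 − 77.6 = 1.4 points.

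**6. Possible bias.** Suppose the removed patients have r times the hazard of the rest and treatment has no effect. A large simulation (400,000 per arm, exponential times, no censoring, Cox model) gives these hazard ratios:

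| Removed | r = 1.5 | r = 2 | r = 3 |
|---|---|---|---|
| 2% | 0.991 | 0.993 | 0.985 |
| 5% | 0.982 | 0.977 | 0.966 |
| 10% | 0.966 | 0.951 | 0.935 |

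The simulation standard error of the log HR is about √(4/800,000) = 0.002, so the first two entries at 2% do not differ meaningfully. At r = 1 there is no bias.

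**The case against.** **The examination may not be an eligibility test.** No passage names it as the test for exclusion 13, which also covers history and risk. It could be a baseline for ocular monitoring. This is fair, but it is a screening procedure, its findings include exactly what exclusion 13 describes, and nothing says its result is to be disregarded for eligibility.

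**Section 8.3 already deals with timing.** Labs and ECOG are listed under Visit 1, with Visit 2 as a fallback, and the randomization code comes last in the Visit 1 list. A pre-dose recheck is ordinary safety practice. This stands in part: the recheck is not a fault. But the schedule allows allocation up to 28 days before dosing, while the 72-hour results can arrive after it.

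**Stronger readings that the documents do not support:**
- A reader might infer that the Visit 2 review also removes patients from ulixertinib only. It covers all criteria, and Section 10.3.4 makes control-arm procedures similar, so it can remove patients from either arm.
- A reader might infer that the ulixertinib arm is selected for better general condition. No lab, ECOG or other general criterion differs by arm. Unequal discretion by unblinded staff is possible, but no text creates it.
- A reader might infer that the PFS comparison ceases to be randomized. The working shows no distortion on that scale, and no document links RVO or CSR to PFS.
- A reader might treat this as independent of the analysis set. It is not: a patient excluded before dosing leaves the comparison only because the FAS requires a dose.

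**Conclusion.** The point holds in limited form. Section 8.3 and exclusion 13 cannot be reconciled with the one-arm eye examination as written, so an exclusion detected only by that examination can occur after randomization in the ulixertinib arm alone and drop out of the primary analysis. Separately, exclusions in either arm can be decided with the allocation known.

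The effect is probably small. Under the assumed 2% to 5% removal and 1.5 to 3 times the hazard, the null HR is about 0.99 to 0.97; it reaches 0.94 only at 10% removed and three times the hazard. These rates and hazards are assumptions.

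SAP Section 7.2 records that the study ended during Part A and that a protocol amendment was expected before Part B. No Part B result is affected; the point concerns the Part B design text and any reuse of it.

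**What to change.** 1. **Re-order.** In the Schedule of Activities, 8.3 and 10.3.1.1, obtain the Part B randomization code only after the final eligibility review, once the labs, ECOG and pregnancy test that decide eligibility are available. Keep the Visit 2 pre-dose check as a safety confirmation. This adds no procedure. It shortens the interval between allocation and first dose.

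2. **Reconcile.** Bring footnote f, 10.3.1.1 and 10.3.4 into line with 8.3 and exclusion 13, so that the criterion is decided before IxRS on the same information in both arms. How this is done clinically is for the sponsor and medical monitor. Examining everyone would add an examination for about 27 to 33 controls per histology. Merely declaring the later examination not to be an eligibility test would not suffice by itself: if a patient is then not dosed, the one-arm loss from the FAS remains.

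3. **Analyze as randomized.** Keep any patient found ineligible after randomization in the Part B PFS analysis in the allocated arm. PFS is now timed from first trial medication, so a never-dosed patient has no start date; Part B would need the randomization date as origin. Section 9.3 would have to be reconciled with continued collection of progression and survival data. The cost is follow-up of a few untreated patients.

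Step 1 alone does not resolve exclusion 13, because an examination tied to the arm cannot precede allocation.

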4 INTRODUCTION

4.1 STUDY RATIONALE

This BVD-523-ABC study builds on the safety and clinical activity experience of previous studies that have evaluated ulixertinib as a novel targeted cancer treatment in cohorts of patients with specific genetic alterations and tumor histologies that result in aberrant MAPK pathway signaling. Early clinical data have demonstrated anti-tumor activity with ulixertinib treatment and have identified specific groups of patients for whom additional development is warranted.

4.2 BACKGROUND

Ulixertinib (BVD-523) is a small molecule inhibitor of extracellular signal-regulated kinase (ERK) family kinases (ERK1 and ERK2) that is being developed as a novel anti-cancer drug (Germann *et al*, 2017; Sullivan *et al*, 2018). ERK kinases are downstream components of the mitogen-activated protein kinase (MAPK) signaling cascade (RAS-RAF-MEK-ERK). Ulixertinib has demonstrated promising early efficacy for patients with tumors harboring alterations in the MAPK pathway, including atypical (non-V600) BRAF alterations, for which there are currently no approved targeted agents. This clinical protocol expands upon the ulixertinib Phase I signal to evaluate the utility of ulixertinib to treat patients with tumors harboring an atypical BRAF alteration. Furthermore, the potential to treat MEK1/2 mutant cancers will also be explored. This patient population is rare (<1% of cancers), however a strong scientific rationale exists to treat patients harboring putatively activating MEK1/2 alterations with ERK inhibition (Emery *et al*, 2017; Gao *et al*, 2018; Yaeger *et al*, 2019).

The MAPK signaling cascade is among the most frequently mutated pathways in human cancer. Approximately 50% of melanoma patients possess a druggable hotspot V600E/K mutation in the BRAF protein kinase. FDA approvals of both immune system- (ipilimumab, nivolumab, and pembrolizumab) and signal transduction-targeted (dabrafenib plus trametinib, vemurafenib plus cobimetinib, and encorafenib plus binimetinib) therapies have greatly expanded the armamentarium available for treating BRAF V600 mutation-dependent cancers.

Atypical BRAF alterations (non-V600) are found in many cancers and are more prevalent than V600 mutations in certain tumor types. For example, between 50–80% of BRAF mutations in non-small cell lung cancer (NSCLC) and 22–30% in colorectal cancer (CRC) encode for BRAF non-V600 alterations (Danker *et al*, 2018). As next generation sequencing becomes standard clinical practice, oncologists are frequently identifying non-V600 BRAF alterations in their patients' tumors. Unfortunately, there are no approved therapies targeting these alterations and thus there remains a lack

of viable therapeutic options that could be employed for optimal treatment of these patients.

From recent studies, a new classification system is emerging for BRAF mutations based on biochemical and signaling mechanisms associated with these mutants (Yao *et al*, 2015; Yao *et al*, 2017; Dankner *et al*, 2018; Yaeger *et al*, 2019). Class I BRAF mutations affect amino acid V600 and signal as RAS-independent active monomers. While ulixertinib has demonstrated activity against MAPK pathway activity initiated by Class I BRAF mutations and thus may offer unique possibilities as single-agent or in combinations, these mutations are currently being addressed clinically with FDA approved inhibitors of BRAF plus MEK (dabrafenib plus trametinib, vemurafenib plus cobimetinib, and encorafenib plus binimetinib).

Class II BRAF alterations function as RAS-independent activated dimers and are not addressed by available approved targeted therapies. Ulixertinib has demonstrated clinical activity against several of these class II BRAF alterations, across multiple tumor types (Sullivan *et al*, 2018).

Class III BRAF alterations exhibit enhanced binding to RAS and wild-type RAF to signal as mutant BRAF-wild-type RAF dimers, thus amplifying the signaling downstream of RAS and thus require upstream activation to drive ERK signaling. For this reason, Class III BRAF alterations commonly co-occur in the context of other drivers of MAPK signaling, e.g. RAS mutation, NF1 loss, RTK activation.

In human tumors the incidence of MEK1/2 mutations is rare (<1%). Similar to BRAF, a mechanism-based classification system has been proposed (Gao *et al*, 2018). Preclinical data has demonstrated activity of ulixertinib in MEK mutant models (Emery *et al*, 2017).

In summary, ulixertinib, is a potent and selective inhibitor of the key MAPK pathway enzymes ERK1 and ERK2, has shown potent anti-tumor effects, including anti-cancer activity using *in vitro* cellular assays and *in vivo* tumor xenograft models. Our initial open-label, first-in-human clinical study (NCT01781429) with oral ulixertinib was conducted to identify the maximum tolerated dose (MTD) and the RP2D. Study aims also included assessment of the PK and pharmacodynamic properties of ulixertinib as well as preliminary efficacy in patients with genetic aberrations in BRAF (both V600 and non-V600 amino acids), NRAS, and MEK. Consistent with current scientific understanding, class II BRAF mutations were demonstrated to be sensitive to single-agent ulixertinib, largely independent of tumor type. In particular, non-V600 BRAF mutations, including G469A/V, L485W, and L597Q, across a variety of solid tumors, were shown to be clinically actionable for the first time, with durable objective responses.

The potential risk profile of ulixertinib is described in further detail in the following sections.

